16. PRIVACY AND CONFIDENTIALITY CONSIDERATIONS INCLUDING DATA ACCESS AND MANAGEMENT

Every effort will be made to protect subject confidentiality. Only the Principal Investigator, the Sub-Investigators, and the research coordinators will have access to the patient's identifying information. All collected participant information will be stored in locked cabinets and maintained in a password protected database in UCSD system. Subjects will be assigned a non-identifiable study number based on order of enrollment. The master-log linking subject PHI with study ID number will be kept separate from other study information, in a password protected document on a limited access drive on UCSD secured computer system, accessible only by [name] and his research staff. Data reported to Circa Scientific, LLC will not contain any PHI. If the results of this study are published, the subject's identity will remain confidential. Records may be viewed by the Sponsor, or their representatives, the FDA, or the UCSD HRPP. However, no personal information about the study subject will be recorded at these times.

Patients who may have any questions or concerns can contact the research team at [contact] or the HRPP.

17. POTENTIAL BENEFITS

The patient may or may not benefit directly from participation in this study. If significant thermal lesions are observed in the esophagus as determined by the gastroenterologist performing the esophagoscopy, the patient will receive the directed to appropriate clinical treatment or follow-up care. It is possible that observation of few or no esophageal lesions will confirm the utility and benefit of the routine use of the Circa™ temperature monitoring probe, and that publication of this data would results in it being disseminated worldwide to benefit other patients undergoing atrial fibrillation, and further reduce the risk of atrio-esophageal fistula formation, a rare, but known and potentially fatal complication of AF ablation.

18. RISK/BENEFIT RATIO

It is possible that identification of few or no esophageal thermal lesions will lead to more widespread use of the Circa™ temperature monitoring probe, and thus reduce the risk of atrio-esophageal fistula, as we believe it has in our laboratory. Furthermore, early identification of any thermal lesions in an individual patient would lead to directed treatment in such an individual subject's case, in this study, possibly preventing progression to a more serious condition. However, the current subjects may derive no direct benefit from this study. The risk of esophagoscopy is low, although there are finite risks, including those noted above in section 14. However, in the assessment of the principal investigator, the benefits outweigh the small risks to the subjects in this study.

19. EXPENSE TO PARTICIPANT

There will be no additional expense to patient for participation in this research study. The cost associated with the esophagoscopy procedure will be paid for by the sponsor, Circa Scientific, LLC. As the ablation and any expenses related to the procedure are standard of care, those costs will be covered by the patient and/or the patient's insurance.

20. COMPENSATION FOR PARTICIPATION

On completion research activities, each participant will be provided \$25 for the inconvenience associated with the research-related procedures. No other compensation will be provided for participation in this study.

23. FUNDING SUPPORT FOR THIS STUDY

This is a single-center, PI initiated study, however the necessary research procedures, including esophagoscopy, are to be funded by the sponsor of this study, Circa Systems, LLC through an OCGA contract.

24. BIOLOGICAL MATERIALS TRANSFER AGREEMENT

Not applicable.

25. INVESTIGATIONAL DRUG FACT SHEET AND IND/IDE HOLDER

Not applicable.

26. IMPACT ON STAFF

Most of the research-related procedures will be performed by the research team (PI, Sub-I's, or study coordinators). However, the Gastroenterology department will be required for the research post-ablation esophagoscopy.

27. CONFLICT OF INTEREST

There is no conflict of interest between the sponsor of this study and the investigators. The Circa™ esophageal temperature probe is already routinely used in all cases during atrial fibrillation ablation at UCSD Medical Center, and the investigators have no ownership interest in the company sponsoring this study, nor have they received in the past or will receive in the future any payments, honoraria, or equivalent from the sponsor.

28. SUPPLEMENTAL INSTRUCTIONS FOR CANCER-RELATED STUDIES

Not applicable.

29. OTHER APPROVALS/REGULATED MATERIALS

Not needed at this time.

30. PROCEDURES FOR SURROGATE CONSENT AND/OR DECISIONAL CAPACITY ASSESSMENT

Not applicable.

DIVISION OF CARDIOVASCULAR MEDICINE
PH [contact]
NIGHTS & WEEKENDS [contact]
FX [contact]

[name]
PROFESSOR OF MEDICINE
CARDIAC ELECTROPHYSIOLOGY
DIRECTOR CCEP PROGRAM
[name]
[name]
[name]
[contact]

Date: 5/29/2021

RE: Circa/EGD Study Statistical Analysis Plan

To whom it may concern:

The SAP for this study protocol is attached (see below).

Sincerely,

A handwritten signature in black ink that reads "[name]".

[name]

For the study population statistical analyses were performed in the following manner:

1. Continuous variables will be expressed as the mean \pm one standard deviation, and statistical analysis for any significant difference will be calculated using the Student's t-test.
2. All categorical variables will be expressed as absolute numbers or percentages, and statistical significance for any significant differences will be calculated using the Chisquared test.
3. A statistically significant difference between variables will require a p value ≤ 0.05 .
4. All statistical analyses will be performed using Microsoft Excel 2010.

Latest Update: 4/28/2021

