In the electrophysiology laboratories at UCSD, where we have performed RFCA for AF and LAAFL for nearly 15 years, in several thousand cases, and to our knowledge have had possibly 1 or 2 atrio-esophageal fistulas (presumed but not confirmed) develop in our patients, over a decade ago. These patients were treated at outside hospitals for associated comorbidities however, which were fatal, and the diagnosis was thus only suspected and not confirmed. Since that time we have always monitored esophageal position and temperature, and then for the last several years since its FDA approval, we have used the Circa™ temperature probe in all our patients and have had no reported cases of atrio-esophageal fistula. We recently began using a newly designed Circa™ probe (see Figure for old and new probe shape) with good results, and plan to evaluate its success in preventing esophageal thermal lesions as well.

Previous studies have suggested that even when one reduces power during ablation at the posterior left atrium and monitors temperature, approximately 27% of patients will develop some evidence of esophageal thermal lesions (including endothelial esophageal ulcers or mediastinal changes). In addition, one center reports an even greater number of lesions observed when using the Circa™ probe during RFCA (although in this study power delivery and temperature were not modulated based on the temperature monitoring during ablation).

In contrast, we believe that due to its sensitivity and ability to monitor esophageal temperature at multiple locations spanning the atrium, use of the Circa™ probe should result in fewer or no esophageal thermal lesions, if esophageal temperature measured by the Circa™ probe is used to guide power delivery and duration of ablation on the posterior left atrial wall.

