8. PROGRESS REPORT

There is a paucity of data in patients on the value of temperature monitoring during RFCA for AF to reduce thermal esophageal injury. However, during the routine clinical use of the device in several hundred cases over the past few years we have clinically observed a marked reduction in ablation time and power delivery in the posterior left atrial wall as compared to prior years before FDA approval of the Circa™ device.

In addition, in some patients we have been unable to ablate critical areas in the left atrium due to such temperature rises observed on the Circa™ probe, and have resorted to having the GI service attending/fellow move the esophagus with an endoscope to the right or left away from the critical ablation sites, thus allowing normal power delivery to achieve transmural atrial ablation and cure AF.

Thus, we believe that by using the Circa™ probe, to guide and limit power delivery and duration of ablation on the posterior left atrial wall, to avoid excessive esophageal temperature rises, and yet successfully complete the ablation, we will limit the potential for any esophageal thermal injury that might lead to an atrio-esophageal fistula.

We have recently completed a non-randomized esophagoscopy study in 20 patients, in whom AF ablation was performed while using the Circa™ probe to monitor and limit luminal esophageal temperature (LET), and thus prevent esophageal thermal lesions. We observed a single possible esophageal thermal lesion in only one patient

undergoing ablation (see progress report Table). This is significantly less than that typically observed in such patients according to previously published studies.

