9. RESEARCH DESIGN AND METHODS

Study Design:

This will be a non-randomized, prospective, single-centered clinical trial. Twenty-five consecutive patients who agree to enroll in the study will undergo their clinically indicated AF ablation, during which all patients will be monitored using the newly designed Circa™ esophageal temperature probe, to prevent luminal esophageal temperature (LET) from rising above 39°C. The day following ablation, patients will undergo esophagoscopy before being discharged from the post-operative recovery area (PTU), in order to determine if there is any evidence of esophageal lesions that might be due to thermal injury.

The gastroenterologist performing esophagoscopy will be blinded to any intra-procedural data during the atrial fibrillation ablation, specifically any data relating to esophageal position during the ablation procedure, any observed temperature rises, and the power and duration of radiofrequency energy delivery during the ablation.

Following endoscopy, all patients will remain in the PTU until recovered from sedation, and when standard criteria are met they will be discharged directly to home and followed up in the outpatient arrhythmia clinic in the same manner as all other patients undergoing AF ablation at UCSD. This routine follow-up process is described to the patient prior to ablation as part of his/her clinical consent for the procedure, and does not involve any research procedures related to this study.

Methods:

The only research component of this study is the post-ablation esophagoscopy which is not standard of care for patients receiving RFCA for atrial fibrillation. The day following the patient's AF ablation, provided there have been no complications and vital signs are stable, he/she will undergo esophagoscopy under sedation, as is standard of care. During this procedure all vital signs will be monitored in a standard manner as they had been during the AF ablation, and the esophagus inspected in a standard manner for any evidence of lesions that might be due to thermal injury. Photographic evidence will be obtained and stored on disk of any lesions observed. A written description of the findings will also be provided by the gastroenterologist in his report of the procedure. Following esophagoscopy the patient will be monitored for the appropriate time to ensure stability of vital signs, and then patient will be discharged home when appropriate criteria are met.

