10. HUMAN SUBJECTS

A total of 25 patients will be recruited from the Cardiology Electrophysiology clinics and PTU, in order to account for any withdrawal. There will be no discrimination in enrollment based on gender or ethnic background. We expect the population of enrolled subjects to reflect similar percentages for gender and ethnicity as the overall population of patients receiving CIED procedures at UCSD. Patients will be approached and consented for the post-ablation esophagoscopy prior to AF ablation. If the eligibility of the subject changes between the time the subject is consented and the procedure, the subject will be considered a screen failure and the subject's participation will not be counted towards accrual for the study. It is the patient's

choice to withdraw from this study at any time before the esophagoscopy, or prior to ablation, without effect on his/her usual clinical care.

Inclusion Criteria: (all must be met)

1. Must have atrial fibrillation and be scheduled for AF ablation.
2. Must agree to esophagoscopy under sedation the next day in order to determine if there is any evidence of esophageal thermal injury.
3. Must give written informed consent.
4. Must be at least 18 years old

Exclusion Criteria: (presence of any one or more)

1. Patient's refusal to participate in the study.
2. Any known esophageal disease or prior injury that would preclude esophagoscopy.
3. Any complications occurring during or after AF ablation that would result in esophagoscopy being an added significant risk to the patient beyond the known potential risks from the esophagoscopy itself.
4. Prior AF ablation

2

Patients seen in the UCSD cardiac arrhythmia clinic or hospital inpatients, who are referred for consideration of AF ablation, will be evaluated to see if they meet enrollment criteria by [name] and/or the co-investigators. Medical records of potential patients will be screened prior to enrollment to ensure eligibility. If eligible, they will be asked if they would like to participate in the study. All patients will be under the care of the cardiac electrophysiology group at UCSD Medical Center.

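### The one-arm SAP gives the esophageal lesion rate no confidence interval and prescribes a chi-squared test without saying what is compared, although very few lesions are expected

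*SAP*

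**What the plan says.** There is one group. Under Study Design in protocol section 9, "all patients will be monitored using the newly designed Circa" probe, and the research procedure is a next-day esophagoscopy for lesions. Section 10 states that "A total of 25 patients will be recruited from the Cardiology Electrophysiology clinics and PTU, in order to account for any withdrawal", so fewer than 25 may be examined. No sample-size calculation, target rate or success rule is given.

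The SAP has four items: mean and standard deviation with a t-test, a rule for categorical data, a 0.05 threshold, and the software. The categorical rule is that "categorical variables will be expressed as absolute numbers or percentages, and statistical significance for any significant differences will be calculated using the Chisquared test". Nothing in the SAP or protocol adds an interval, a comparator or a one-sample or two-sample form, and the SAP does not single out the lesion rate.

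Two numerical rates appear in the protocol as context. Section 7 reports that "approximately 27% of patients will develop some evidence of esophageal thermal lesions (including endothelial esophageal ulcers or mediastinal changes". Section 8 describes the centre's completed 20-patient esophagoscopy study: "We observed a single possible esophageal thermal lesion in only one patient". It adds: "This is significantly less than that typically observed in such patients according to previously published studies". That sentence gives no rate, test or interval. Section 7 also mentions, without a figure, one centre that saw more lesions with this probe when power was not adjusted to temperature. Section 17 says: "It is possible that observation of few or no esophageal lesions will confirm the utility and benefit of the routine use". The word few is not defined.

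**The concern.** With no control group, the main product of the study is an estimate of one proportion, and at about 25 patients its uncertainty is wide. A report of 0% or 4% without an interval invites a stronger reading than the data allow, especially beside the section 17 statement on utility and benefit.

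The second problem is the test. A chi-squared test needs something to compare. If that is a published rate, or the earlier cohort, the investigators' hope of few or no lesions puts the data where the chi-squared approximation is weakest. A p-value near 0.05 can then fall on either side of the threshold according to the test used.

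**Working it through.** **Inputs.** 25 recruited (section 10); about 27% (section 7), treated as fixed because no denominator is given; 1 of 20 (section 8); threshold 0.05 (SAP item 3), taken as two-sided because the SAP does not say. The number examined is not stated, so values below 25 are assumptions.

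**The plan's own figures.** The 25 has no stated inputs and cannot be reproduced. The one inferential statement, on 1/20, can be checked if its unnamed reference is taken to be 27%: exact binomial p = 0.023, chi-squared p = 0.027, exact 95% interval 0.1% to 24.9%. On that assumption it holds.

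**Intervals at 25 examined.** The Clopper-Pearson limits for x of n are the 0.025 quantile of Beta(x, n − x + 1) and the 0.975 quantile of Beta(x + 1, n − x). For 0/25 the upper limit is 1 − 0.025^(1/25) = 13.7%.

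| Lesions/25 | Exact 95% interval | vs 27%: chi-squared p | vs 27%: exact p | vs 1/20: chi-squared p | vs 1/20: Fisher p |
|---|---|---|---|---|---|
| 0 | 0 to 13.7% | 0.002 | 0.0005 | 0.26 | 0.44 |
| 1 | 0.1 to 20.4% | 0.010 | 0.006 | 0.87 | 1.00 |
| 2 | 1.0 to 26.0% | 0.032 | 0.040 | 0.69 | 1.00 |
| 3 | 2.5 to 31.2% | 0.091 | 0.114 | 0.41 | 0.62 |

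Chi-squared is uncorrected, as the SAP mentions no correction. Against 1/20, the smallest expected count is 0.4 to 1.8 for 0 to 3 lesions. For 0/25, the single lesion among 45 patients falls in the earlier group with probability 20/45 = 0.44, which is the Fisher p-value. So not even zero lesions could be shown to be lower than 1/20.

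**Where the named test and an exact test part.**

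- *2/23 against 27% (23 examined is assumed).* Expected counts are 23 × 0.27 = 6.21 and 16.79. Chi-squared = 4.21²/6.21 + 4.21²/16.79 = 2.854 + 1.056 = 3.91, p = 0.048. The exact lower tail is P(X ≤ 2) = 0.032. Adding the upper-tail outcomes no more likely than 2 (X ≥ 11, 0.026) gives p = 0.058. The exact upper limit is 28.0%, above 27%. For two lesions this split occurs at 23. At 24 and 25 both tests are significant, and at 22 neither is (0.058 and 0.089).
- *7/25 against 1/20.* Expected lesion counts are 25 × 8/45 = 4.44 and 20 × 8/45 = 3.56. Chi-squared = 4.02, p = 0.045; Fisher p = 0.059.

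**Sensitivity to the reference.** At 25 examined, the largest count whose exact upper limit lies below the reference is 0 for 20%, 2 for 27% and 3 for 35% (upper limits 13.7%, 26.0% and 31.2%). The 20% and 35% are assumed, to show the range.

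**The case against.** The aim is only to evaluate effects, no formal hypothesis is stated, and the t-test and chi-squared items may be meant for comparisons within the cohort. SAP item 2 also allows counts, and any reader with a count and a denominator can compute the exact interval. Both points are fair. But if the tests are only for subgroups, the lesion rate has no inferential plan at all, and a reader still cannot tell what comparison, if any, was intended.

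A reader might also infer that the two rates in the protocol give conflicting answers, so that the choice of reference decides the conclusion. The documents do not support that. Sections 7 and 8 set expectations against published experience and offer 1/20 as prior experience, not as a benchmark. For 0 to 2 lesions, being below 27% and being indistinguishable from 1/20 are both true; the second mainly reflects low power with one event in 20 patients. For 3 to 6 lesions neither comparison is significant. Nor can one say that only the reference matters and the test form does not: that fails at 2/23, and section 10 foresees withdrawals. Nothing shows that a reference will be chosen after the count is seen; the plan merely leaves this open.

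**Conclusion.** The point stands in this form: the main outcome of a one-arm study has no planned interval, and the named test has no stated comparison and is unreliable at the counts expected. Omitted upper limits are 13.7%, 20.4% and 26.0% for 0, 1 and 2 lesions in 25. The wrong-side-of-0.05 examples (2/23 and 7/25) are specific counts, not a general failure: against 27% with all 25 examined, chi-squared and exact tests agree for 0 to 4 lesions.

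The comparisons with 27% treat it as fixed and like-for-like. It may not be, because it includes mediastinal changes, whereas this study inspects the esophagus by esophagoscopy. The exact intervals need neither assumption.

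This should be fixed. It does not invalidate the study, whose data are unaffected.

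**What to change.** In the SAP:

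- Make the primary result the proportion of ablated and examined patients with at least one esophageal lesion, with a two-sided Clopper-Pearson 95% interval at the number actually examined. Report how many were ablated but not examined, and why.
- If a comparison is wanted, name one reference, with its lesion definition and justification. Use an exact binomial test for a fixed rate or Fisher's exact test for an earlier cohort. Claim a rate lower than a fixed reference only if the exact upper limit lies below it.
- Fix the reference before the data are analysed, or label the comparison post hoc. The SAP is dated 2021 and opens with "For the study population statistical analyses were performed in the following manner" but then uses the future tense, so the post hoc label may be needed. The interval is valid either way.
- Otherwise restrict the t-test and chi-squared items to descriptive within-cohort comparisons, with Fisher's test where expected counts are small.

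In protocol section 17, say that a low rate would be consistent with benefit rather than confirm it, since there is no concurrent control. The existing hedge at the start of that sentence does not cover this.

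The cost is a few lines of text and one exact calculation, with no new patients or data. The price is a more modest headline: 0% becomes 0% with an upper limit of about 14%. A like-for-like esophagoscopy rate must come from sources outside these documents; if none can be justified, the report should be an estimate only.

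### Minor: the SAP names only the chi-squared test and has no small-count rule, although 25 patients are likely to yield only about 0 to 2 with a lesion

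*SAP*

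**What the plan says.** SAP item 2 covers every categorical variable with one test: "statistical significance for any significant differences will be calculated using the Chisquared test". Item 3 adds: "A statistically significant difference between variables will require a p value ≤ 0.05". Item 4 names only the software: "All statistical analyses will be performed using Microsoft Excel 2010". Neither document mentions an exact test, a continuity correction or a minimum expected count, and neither says which categorical variables will be compared or between which groups.

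The protocol describes a single group (section 9): "Twenty-five consecutive patients who agree to enroll in the study will undergo their clinically indicated AF ablation". Section 7 expects that use of the "probe should result in fewer or no esophageal thermal lesions". It also cites a literature rate: "approximately 27% of patients will develop some evidence of esophageal thermal lesions". Section 8 reports the centre's earlier series of 20 patients: "We observed a single possible esophageal thermal lesion in only one patient".

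**The concern.** The chi-squared p-value is a large-sample approximation. With one or two lesions among 25 patients, any 2×2 table of lesion status by a patient or procedural category has at least one expected count below 1, where the approximation is poor. The SAP permits testing of categorical variables without restriction, and comparing patients with and without lesions is an obvious use of that permission. One lesion that happens to fall in a patient with an uncommon characteristic could then be reported as a statistically significant association. The result would also depend on whether the analyst applied a continuity correction, which the SAP leaves open.

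**Working it through.** The SAP and protocol give no figure on this point to reproduce, so the check starts from their inputs.

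**Inputs.** N = 25 (protocol section 9). Earlier series 1/20 = 5% (section 8). Literature rate 27% (section 7). Threshold p ≤ 0.05 (SAP item 3). Assumptions: all 25 are evaluable, and a binary trait is held by m patients, m = 1 to 12.

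**Expected number of lesion patients.** At 5%: 25 × 0.05 = 1.25. Binomial(25, 0.05) gives P(0) = 0.277, P(1) = 0.365 and P(2) = 0.231, in total 0.873. The 5% is itself uncertain: the exact 95% interval for 1/20 is 0.1% to 25%.

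**Smallest expected count**, with L lesions = m × L / 25. With m = 12 this is 0.48 for one lesion and 0.96 for two. At 27%, 25 × 0.27 = 6.75 lesions are expected and the smallest count is at most about 3.4 (half of 6.75), still below 5.

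**One worked table.** One lesion, in a trait carrier, with m = 5: 1/5 against 0/20.
- Uncorrected chi-squared = N(ad − bc)² / (product of the four margins) = 25 × (1 × 20 − 4 × 0)² / (5 × 20 × 1 × 24) = 10,000 / 2,400 = 4.17, p = 0.041.
- Yates: 25 × (20 − 12.5)² / 2,400 = 0.586, p = 0.44.
- Fisher: the chance that the single lesion falls among the 5 carriers is 5/25 = 0.20.

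**All tables with one or two lesions, m = 1 to 12.** Uncorrected chi-squared gives p ≤ 0.05 in 15 tables. Fisher exceeds 0.05 in these 9:

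| Lesions | Trait held by (m) | Lesions in carriers | Chi-squared p | Fisher p |
|---|---|---|---|---|
| 1 | 2 | 1 | 0.0005 | 0.080 |
| 1 | 3 | 1 | 0.0057 | 0.120 |
| 1 | 4 | 1 | 0.019 | 0.160 |
| 1 | 5 | 1 | 0.041 | 0.200 |
| 2 | 1 | 1 | 0.0005 | 0.080 |
| 2 | 2 | 1 | 0.022 | 0.157 |
| 2 | 7 | 2 | 0.018 | 0.070 |
| 2 | 8 | 2 | 0.032 | 0.093 |
| 2 | 9 | 2 | 0.049 | 0.120 |

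In the other 6 the two tests agree, counting Fisher p of exactly 0.05 (two lesions, m = 6: 15/300) as significant. Yates is significant in 5 of the 15, and Fisher agrees in all 5.

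**False-positive rate of uncorrected chi-squared.** Each table is weighted by Binomial(25, rate) for the lesion count, times the hypergeometric probability given m. For m = 5 at a 5% rate: one lesion 0.365 × 0.200 = 0.0730; two 0.231 × 0.0333 = 0.0077; three 0.0930 × (0.0870 + 0.0043) = 0.0085; four or more about 0.0007; total 0.090.

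| Lesion rate | m = 1 | 2 | 3 | 4 | 5 | m = 6 to 12 | Mean over 1 to 12 |
|---|---|---|---|---|---|---|---|
| 5% | 5.0% | 6.7% | 5.1% | 7.1% | 9.0% | 0.3–3.2% | 3.6% |
| 10% | 9.2% | 6.7% | 4.7% | 6.7% | 7.6% | 1.8–4.6% | 4.7% |
| 20% | 9.2% | 5.0% | 4.3% | 5.3% | 4.7% | 3.7–5.6% | 5.0% |
| 27% | 4.9% | 5.6% | 3.7% | 4.6% | 4.3% | 4.3–6.2% | 4.8% |

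Fisher's actual rate over the same m is 0.05–1.5% at a 5% lesion rate and at most 3.1% at 27%.

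**Comparisons that the protocol text does point to.** Against 27%, with expected counts 6.75 and 18.25 (chi-squared / exact binomial): 0 lesions 0.002 / 0.0005; 1, 0.010 / 0.006; 2, 0.032 / 0.040; 3, 0.091 / 0.114; 4, 0.22 / 0.27; 5, 0.43 / 0.51. The verdicts agree throughout. Against 1/20 (chi-squared / Fisher), neither is significant for 0 to 6 lesions (at 6, 0.081 / 0.112). The first disagreement is at 7 lesions, 0.045 / 0.059.

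**The case against.** No lesion-by-trait comparison is planned anywhere; the table that causes trouble is hypothetical, and the larger gap is that the SAP names no comparison at all. That is true, and it is why the point is conditional and minor. The SAP nevertheless sets one test and one threshold for all categorical variables. At either lesion rate the protocol cites, a split by lesion status would be expected to have a count below 5.

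A disagreement with Fisher does not show that chi-squared is wrong. Averaged over trait frequencies, its false-positive rate is 3.6% to 5.0% at the four lesion rates examined, so part of the gap in p-values is Fisher's own conservatism. This also stands. What remains is inflation, up to about 9%, for traits shared by about five or fewer patients when lesions are rare. The 9 of 15 is a count of tables, not a probability.

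The disagreement depends on the uncorrected form; with Yates' correction it vanishes. Since the SAP does not say which form applies, two analysts following it could reach opposite conclusions.

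With no lesions (probability 0.277 at a 5% rate) no such test can be computed, and at lesion rates of 20–27% the inflation mostly disappears. Both points limit how often the problem would arise.

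**Conclusion.** The concern holds as a minor one. SAP item 2 applies a large-sample test without a small-count rule to data likely to contain very few lesions. In the clearest case an event with a 20% chance of arising by coincidence would be called significant at p = 0.041. The size is modest: at a 5% lesion rate the false-positive rate is 5.0–9.0% for traits held by one to five patients and below nominal for six to twelve.

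This rests on three assumptions: that lesion status is in fact compared across categories, that the uncorrected test is used, and that lesions are about as rare as the 1/20 series suggests. The comparison with 27% gives the same verdict by chi-squared or an exact test for 0 to 5 lesions, as does the comparison with the earlier series for 0 to 6.

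**What to change.** Keep item 2 as it stands and add after it:

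> For two-group comparisons in which any expected count is below 5, two-sided Fisher's exact test will be used instead of the chi-squared test. Comparisons of patients with and without an esophageal lesion are exploratory; their p-values will be reported descriptively and the threshold in item 3 will not be applied to them.

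The two sentences overlap for lesion tables, harmlessly: the first gives a valid p-value, the second stops it being read as a verdict. The second also covers continuous variables compared by lesion status under item 1.

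The cost is small. No new data are needed, and the p-value is a sum of hypergeometric probabilities. Chi-squared stays available for larger counts and for a one-sample comparison. In lesion tables it would rarely be used: with a trait in at most 12 of 25 patients, 12 × L / 25 ≥ 5 requires 11 or more lesions.

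The downside is low power. With one lesion, Fisher reaches 0.05 only if the trait separates exactly that patient from the other 24 (p = 0.04). The change does not supply the missing named comparison, which needs its own remedy. The SAP is dated 2021 and its lead-in is in the past tense; if the analyses are already done, the change should be labelled post hoc.
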